6. STATISTICAL PLAN AND CONSIDERATIONS

For assistance with plans for biostatistics in this research, please visit the Department of Health Studies at www.health.bsd.uchicago.edu.

Discuss the following in detail:

- a) **Sample size determination**— Our sample size of twenty (20) patients is justified in that we believe recruitment can be accomplished within 9 months. True pace of recruitment/refusal/crossover will drive the timeline of a future full-scale study, and may influence inclusion/exclusion criteria of the full-scale study.
- b) **Power analysis or considerations**— Results of the study (i.e. the calculated ADC threshold) will be used to drive a power analysis for a future larger study to determine if addition of DW-MRI to the care paradigm results in clinically meaningful improvement in care.
- c) Statistical methods: **DW-MRI differentiation metrics and abscess characterization**
 - *Qualitative analysis:* The collection will be presented to two separate radiologists who will be blinded to patients' history, laboratory results, findings from other imaging modalities, and final diagnosis. They will independently review the MR images for detection of collections (T2-weighted images together with diffusion-weighted images and ADC maps (T2 + DW-MRI). ADC maps will be generated for each patient using a home grown software. Each radiologist will assign a score from a five-point scale (1 = no abscess; 2 = probably not an abscess; 3 = equivocal; 4 = possible abscess; 5 = definite abscess) based on the level of confidence in the diagnosis for each review session. A score of 4 or 5 will be considered as positive for diagnosis of abscess for each case.
 - *Quantitative analysis:* Following qualitative analysis, the same two radiologists independently will measure ADC of the collections in each patient on ADC maps. Mean and 10th percentile ADC values will be computed by placement of region of interest (ROI) on ADC maps using DW images as guide. Each ROI will be placed in the center of the

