collection over the darkest pixels on ADC maps keeping size as large as possible and avoiding the volume averaging from the surrounding tissue. The reference standard for the diagnosis of abscess will be based on the analysis of aspiration fluid from the collection. *Statistical analysis:* For statistical analyses, a software package (SPSS 11.0 for Windows; SPSS Inc., Chicago, IL, USA) will be used. Sensitivity and specificity of each review session for each radiologist will be calculated. McNemar's test will be used for multiple comparisons of sensitivity of different review sessions. Confidence score of each review session will be compared using Wilcoxon-signed rank test. Two-tailed Student's *t* test will be used for comparison of ADC values. A two-tailed *p* value of less than 0.01 will be considered to indicate a statistically significant difference. Simple κ coefficients will be used to assess interobserver agreement for confidence score and ADC measurements. An ROC curve will be constructed for ADC values, and area under the curve measured the overall ability of ADC in differentiation of abscess from non-infected collections.

d) Subject Population(s) for Analysis

- *All-imaged population:* Any subject who underwent DW-MRI in the post-operative setting after identification CT-proven intrabdominal collection > 3 cm in average diameter, whom the surgeon determines based on best clinical practice that percutaneous drainage is indicated.

e) If any Intent to Treat Analysis will be done on subjects withdrawing before completion or those who remained in the study but withdrew from intervention, please describe in detail: Not applicable

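### The signed-rank test compares a directional abscess score between review sessions without splitting by true status, so read as written it tests net drift, not better discrimination

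*Combined protocol and SAP*

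**What the plan says.** Section 6c, Qualitative analysis, has two blinded radiologists score each collection on a scale with "1 = no abscess; 2 = probably not an abscess; 3 = equivocal; 4 = possible abscess; 5 = definite abscess". It adds that "A score of 4 or 5 will be considered as positive for diagnosis of abscess for each case". The score therefore expresses how likely an abscess is, not how sure the reader is of whichever diagnosis was made.

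Under Statistical analysis, the same section says: "Confidence score of each review session will be compared using Wilcoxon-signed rank test". The Study Summary repeats this. Neither place mentions the aspirate result, a recoding of the score, or a restriction to infected cases. Section 6d defines one analysis population, which opens "Any subject who underwent DW-MRI in the post-operative setting" and takes infected and sterile collections together.

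Three neighbouring provisions matter. Sensitivity and specificity are calculated for each session and each radiologist. McNemar's test compares sensitivity between sessions, and nothing compares specificity. The ROC curve is planned for ADC values, not for the five-point score. The reference standard is the analysis of the aspirated fluid.

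**The concern.** Objective 2 asks what best separates sterile from infected collections, and Objective 3 aims to prevent drainage of sterile ones. A session that serves those aims moves scores apart: up where the collection is infected, down where it is sterile. A signed-rank test on the raw score over both groups asks whether the scores went up or down on balance.

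Two errors can follow. A real gain in discrimination may show no difference. A session in which readers simply call more collections abscess may show a clear one, although that shift is the overtreatment the Background sets out to reduce. The pilot is meant to shape a larger study, so either misreading could carry forward.

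**Working it through.** **Inputs.** N = 20 (section 6a; the rationale is "Our sample size of twenty (20) patients is justified in that we believe recruitment can be accomplished within 9 months", with no power figure). Two-sided level 0.01 (section 6c: a "value of less than 0.01 will be considered to indicate a statistically significant difference"). The plan gives no expected infected-to-sterile mix. Section 1A cites up to 40% sterile for rim-enhancing collections, which would be 0.40 × 20 = 8 sterile and 12 infected. This is an assumption, so the mix is varied below. The plan states no result for this test, so there is none to reproduce.

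**Step 1: what the pooled test responds to.** If n₁ infected cases move up by a and n₀ sterile cases move down by b, the mean change is (n₁a − n₀b)/N. Correct movement in sterile cases enters with a minus sign.

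**Step 2: every read improves by one point.** All changes have size 1, so all ranks tie and the exact test reduces to a binomial: p = 2 × P(X ≥ n₁), X ~ Bin(20, 0.5). For 12:8, p = 2 × 263,950/1,048,576 = 0.50. For the normal approximation, each mid-rank is 10.5, so W⁺ = 126, the mean is 105 and the SD is √(20 × 10.5²/4) = 23.48. Then z = 0.89 and p = 0.37.

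| Infected:sterile | Exact p | Normal approx. p |
|---|---|---|
| 10:10 | 1.00 | 1.00 |
| 12:8 | 0.50 | 0.37 |
| 14:6 | 0.115 | 0.074 |
| 15:5 | 0.041 | 0.025 |
| 16:4 | 0.012 | 0.007 |
| 17:3 | 0.0026 | 0.0018 |
| 18:2 | 0.0004 | 0.0004 |

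**Step 3: two constructed cases at 12:8.**
- *Genuine gain.* All 20 score 4 in one session. In the other, infected cases score 5 and sterile cases 3. Specificity goes from 0/8 to 8/8 and the AUC of the score from 0.5 to 1.0. The pooled signed-rank p is 0.50. Sensitivity is 12/12 both times, so McNemar's test has no discordant pairs. Neither planned between-session test registers the gain.
- *No gain.* All 20 move from 3 to 4. The AUC stays at 0.5 and specificity falls from 8/8 to 0/8. The signed-rank p is 2 × 0.5²⁰ = 0.0000019, and McNemar's exact p on sensitivity is 2 × 0.5¹² = 0.0005. Both are significant.

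**Step 4: where the offset fails.** With 12 infected at +2 and 8 sterile at −1, the mid-ranks are 14.5 and 4.5, so W⁺ = 174 and W⁻ = 36, and exact p = 0.005. With 12 infected at +1 and 8 sterile unchanged, exact p = 2 × 0.5¹² = 0.0005.

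**Step 5: does reversing the sign in sterile cases cure it?** For the uniform improvement, all 20 changes become positive and p = 0.0000019. But if every score rises by one point at 16:4, the reversed changes are 16 positive and 4 negative, giving exact p = 0.012 (approximation 0.007). At 17:3, exact p = 0.003. With few sterile cases, a sign-reversed test can still credit calling everything abscess.

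**Step 6: separate strata.** With n cases all moving the same way, the smallest exact p is 2 × 0.5ⁿ: 0.0078 for n = 8 and 0.0156 for n = 7. A stratum of 7 or fewer cannot reach p < 0.01.

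**The case against.** **Pooling is inferred.** The plan does not say that the test runs over all patients. The sentence before it compares sensitivity, which uses infected cases only, so a restricted comparison is not ruled out. This stands as a limit on the wording. The text still offers no split and only one population, so the pooled reading is the natural one.

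**Almost no power.** A reader might infer that the test could hardly ever show an improvement. The documents do not support that. The 40% is an upper figure for rim-enhancing collections, while this cohort is selected by surgeons as needing drainage, and section 1A says surgeon suspicion helps predict abscess. The sterile share may be lower. The earlier gain from DW-MRI that the protocol cites is described as better abscess detection, which is upward movement in infected cases. In both situations the pooled test can reject (steps 2 and 4).

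**Overtreatment would pass unseen.** A reader might infer this too, but specificity is calculated for each session, so sterile cases pushed to 4 or 5 would show as lost specificity. What remains is that specificity is not compared between sessions, and that movement within scores 1 to 3 or between 4 and 5 leaves it unchanged.

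**The comparator is missing.** Section 6c describes one image set, T2 with DW-MRI, and names no second session. The test cannot be run until one is named. The problem with the score remains whichever sessions are chosen.

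**Little rests on it.** Sections 2f and 5b make the ADC threshold the primary output, this is a hypothesis-generating pilot, and DW-MRI does not guide care of its subjects. This stands and limits the importance of the point.

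**Conclusion.** The point holds in a limited form. Read as written, the signed-rank comparison measures net drift in a likelihood-of-abscess score and does not measure discrimination. For a uniform one-point improvement, exact p is 0.50 at 12:8 and 0.012 at 16:4, against a level of 0.01. A uniform upward shift gives p = 0.0000019.

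These sizes rest on an assumed mix, on equal movement in both groups and on the pooled reading. With 15% or fewer sterile collections, or larger moves in infected cases, the test can reach significance, though it still does not measure discrimination. No other planned between-session comparison fills the gap, because only sensitivity is compared and the ROC analysis covers ADC only. It is a secondary reader analysis. The plan should be changed, but the primary output is not affected.

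**What to change.** In section 6c and the Study Summary:

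1. Name the sessions to be compared. Only T2 with DW-MRI is described, so the comparator must be stated.
2. Report the signed-rank comparison of scores separately in infected and sterile collections, as defined by the aspirate result.
3. Make the between-session comparison of discrimination the paired difference in AUC of the five-point score against the aspirate result, with a confidence interval, for each radiologist. Unlike the raw score, the AUC does not improve when every score rises together.
4. Compare specificity as well as sensitivity between sessions.
5. Do not rely on a sign-reversed pooled test alone, for the reason in step 5.

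Cost: a few sentences in two places. The reference label is already planned, so no new data are needed if a second read is already intended; if not, naming the comparator adds a reading session. Downside: the sterile group will be small, and with 7 or fewer cases it cannot reach p < 0.01, so its results should be treated as descriptive.

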- c) **Past research and/or preclinical data**—Oto *et. al.* have identified a novel method using diffusion weighted magnetic resonance imaging (DW-MRI) of abdominopelvic collections that can perfectly discriminate abscesses from ascites with a threshold apparent diffusion coefficient (ADC) of $2.0 \times 10^{-3} \text{ mm}^2/\text{s}$ (i). It is important to note this study *did not* include collections identified in the post-operative setting; it is unclear whether inflammatory fluid or presence of blood may diminish this discrimination. If the discriminatory capacity is *not* diminished, then clearly DW-MRI has great potential within the diagnosis and treatment of post-operative abscess formation in colon and rectal resection.
 - d) **Rationale for conducting this research**— Further investigation is required in order to determine whether DW-MRI is applicable in the evaluation of post-operative collections, and whether utilization of DW-MRI can enhance application of percutaneous drainage and prevent unnecessary drainage. DW-MRI is well established in the identification and management of brain abscesses. Oto *et. al.* have already demonstrated the utility of DW-MRI in discriminating abdominopelvic abscess from ascites. They compared ADC values of abscess and non-infected ascites in 58 patients. Compared to T2-weighted images alone, addition of DW-MRI images allowed for nearly 100% detection of abscesses. Further, a cutoff ADC value of $2.0 \times 10^{-3} \text{ mm}^2/\text{s}$ allows for perfect discrimination between abscess and non-infected ascites (Oto), thereby increasing the abscess detection rate (**Fig. 1** (Fig . 7 from Oto *et. al.*)) and potentially minimizing unnecessary percutaneous aspiration or drainage.
 - e) **Dose rationale and risks/benefits (as applicable)** – Not applicable

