field of view = 30–38 cm, receiver bandwidth = 64 kHz, a parallel imaging reduction factor of 2, one signal acquired, section thickness = 5 mm, section interval = 2.5 mm) . These images will be obtained through the known location of the abscess based on previous CT examination. The total duration of MR scan time will be 25 minutes or under. We will optimize our protocol by scanning two volunteers and test different SENSE, TR/TE and NEX parameters for an optimum protocol.

- d) **Summary of sequence and duration of all study periods:** The project duration is estimated at one year. Based on the pilot data, the investigators will commit to submitting a full grant application within 3 months of completing the pilot data project.
- a. *Month 1 – 9: Patient accrual:* The Section of Colon and Rectal Surgery is committed to recruiting twenty (20) patients within this timeframe who have undergone colon or rectal resection including appendectomy and who through usual clinical processes have undergone cross-sectional imaging in the form of CT, with a discrete abdominopelvic abscess >3 cm in average diameter identified. The patients will then be put through the pilot protocol as above (see Objective 3 and **Fig. 2**).
 - b. *Month 10-12: Data analysis and assessment:*
 - i. Objective 1: The protocol will be validated for efficacy and cost, with the primary endpoint being ability to report an ADC value for a collection identified on prior CT through use of the DW-MRI protocol.
 - ii. Objective 2: DW-MRI readings will be analyzed and ADC values will be compared and validated in an attempt to report a threshold ADC that reliably discriminates sterile and infected post-operative fluid collections.
 - iii. Objective 3: Determine the effect size from utilization of DW-MRI (defined as a change in management decision to pursue drainage or hold on drainage)
 - iv. Global Assessment: Determine whether the outcome measures are appropriate, reliable, and feasible. Finalize eligibility criteria for a larger study. Generate hypothesis and determine sample size calculation for larger study.
 - c. The investigator team will meet at 2-month intervals for a research in progress meeting to discuss accrual logistics and problem areas in order to fine tune the study protocol, and identify key parameters that will require adjustment prior to submission of a full grant application.
- e) **Discuss randomization processes and use of controls or placebos, as applicable:** Not applicable

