5. STUDY PROCEDURES

- a) Please see patient flow (**Figure 2**) as well as study design.
- b) This is a single point intervention (DW-MRI acquisition) within the context of a usual clinical care pathway. The results of the DW-MRI will not be utilized for clinical decision making for the subjects in the study. Primary output measures are ADC threshold to discriminate sterile from infected post-operative fluid collections which may be used to guide a larger prospective study.
- c) Labs, diagnostic testing, post-operative visits, and further intervention will be at the discretion of the surgeon based on usual best clinical care and not directly born of the study intervention (i.e. not research related).
- d) **Methods and procedures:** See 'MRI acquisition' above under Study Design.

- e) **Scales/assessments:** None
- f) **Examinations:** None related to this single-point intervention
- g) **Questionnaires:** None
- h) **Labs to be conducted:** None related to this single-point intervention
- i) **Plan for unscheduled visits:** None related to this single-point intervention
- j) **Contact between study visits:** None specifically research related. Patients will undergo usual post-operative care.
- a) **Future contact regarding research studies:** None specifically research related. Patients will undergo a routing post-operative visit or visits at the discretion of their treating surgeon.

Refer to [SCHEMA](#) in Appendix B.

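### Simple kappa is the wrong agreement statistic for ADC, a continuous measurement: with no categories or cut-off stated, its value is set largely by how the readings are rounded

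*Combined protocol and SAP*

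**What the plan says.** Section 6c (Statistical analysis) states: "Simple κ coefficients will be used to assess interobserver agreement for confidence score and ADC measurements". The Statistical Methodology entry of the Study Summary repeats it.

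The two measures in that sentence are of different kinds. The confidence score is a five-point scale with a stated positivity rule: "A score of 4 or 5 will be considered as positive for diagnosis of abscess for each case". For ADC, section 6c (Quantitative analysis) says "the same two radiologists independently will measure ADC of the collections in each patient on ADC maps" and "Mean and 10th percentile ADC values will be computed by placement of region of interest (ROI) on ADC maps". No categories, cut-off or rounding unit are given for the ADC agreement analysis. Elsewhere in 6c the plan treats ADC as continuous, with a t test and an ROC curve.

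Two other statements bear on the use of the result. Section 5b says "Primary output measures are ADC threshold to discriminate sterile from infected post-operative fluid collections". The Global Assessment in section 2d sets the pilot this task: "Determine whether the outcome measures are appropriate, reliable, and feasible".

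**The concern.** Simple (unweighted) kappa is defined for categories. It credits a pair of readings only when both fall in the same category, and every other pair counts as full disagreement. Applied to ADC as recorded, each distinct value is its own category, so a difference of 0.01 × 10⁻³ mm²/s is penalised as heavily as a difference of 2.0. The number of decimals kept then becomes the category definition, and the plan leaves it open.

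The primary output is an ADC threshold, so the pilot needs to know how far two readers differ in ADC units, and whether one reads systematically higher. Kappa gives neither. Close readers could be reported as having almost no agreement. Choosing a coarser rounding after the readings are seen could also make agreement look high.

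**Working it through.** The plan states no kappa, ICC or precision target for reader agreement, so there is no figure of its own to reproduce. The check asks what the stated rule returns when followed literally.

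**Inputs** (ADC in units of 10⁻³ mm²/s)
- 20 patients and two independent readers (section 6).
- 12 abscesses and 8 sterile collections: an assumption, taken from the 40% sterile share quoted in section 1A (0.40 × 20 = 8).
- True ADC: abscess 1.17 ± 0.42, sterile 3.57 ± 0.68 (Figure 1, observer 1, where the comparison group is non-infected ascites).
- Reader error: independent, normal, without bias, SD 0.05 to 0.50. This is an assumption, because the documents give no reader error.

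**Formulas**
- Kappa = (pₒ − pₑ) / (1 − pₑ), where pₒ is the observed and pₑ the chance proportion of identical categories.
- Expected identical pairs at two decimals = 20 × 0.01 / (2√π × SD). At SD 0.10 this is 0.2 / 0.354 = 0.56, so fewer than one pair in 20 matches.
- Limits of agreement around the bias = ±1.96 × SD of the reader differences. At SD 0.10 theory gives 1.96 × √2 × 0.10 = 0.28; the simulated average from 20 pairs is 0.27.
- ICC ≈ between-collection variance / (that variance + SD²). The pooled variance is 0.6 × 0.42² + 0.4 × 0.68² + 0.6 × 0.4 × (3.57 − 1.17)² = 0.106 + 0.185 + 1.382 = 1.673. At SD 0.10, 1.673 / 1.683 = 0.994.

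**Results** (averages over 3,000 simulated studies)

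| Reader SD | Kappa, 2 decimals | Kappa, 1 decimal | Kappa, whole units | Kappa, split at 2.0 | ICC | Limits |
|---|---|---|---|---|---|---|
| 0.05 | 0.05 | 0.46 | 0.92 | 0.99 | 0.999 | ±0.14 |
| 0.10 | 0.02 | 0.24 | 0.84 | 0.98 | 0.994 | ±0.27 |
| 0.20 | 0.01 | 0.11 | 0.69 | 0.95 | 0.977 | ±0.55 |
| 0.50 | 0.004 | 0.04 | 0.35 | 0.79 | 0.87 | ±1.37 |

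Along each row the readings are the same and only the categories change. At SD 0.10 that alone moves kappa from 0.02 to 0.98. Down the two-decimal column, a tenfold change in reader error moves kappa only from 0.05 to 0.004, so it barely separates good readers from poor ones. At coarser rounding kappa does respond to reader error, but its level still depends on the unit chosen.

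**Sensitivity**
- *Less separation between groups.* Figure 1 does not come from post-operative collections, and section 1A says of such fluid that "it is unclear whether inflammatory fluid or presence of blood may diminish this discrimination". With the sterile mean lowered to 2.5 or 2.0 at reader SD 0.10, kappa is 0.02 at two decimals, 0.23–0.24 at one, 0.81–0.83 at whole units and 0.88–0.93 split at 2.0. The ICC is 0.98 and the limits stay at ±0.27.
- *Systematic reader differences.* The Figure 1 observer means differ by 1.43 − 1.17 = +0.26 for abscess and 3.42 − 3.57 = −0.15 for ascites. Adding these shifts at SD 0.10 gives kappa 0.01, 0.07, 0.69 and 0.91 in the same order, ICC 0.976, and 1.96 × SD of the differences of about 0.48.
- *Case mix.* Splits of 10/10 and 16/4 at SD 0.10 give kappa 0.02, 0.23–0.24, 0.82–0.85 and 0.96–0.98, with ICC 0.991–0.994.

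The dependence on rounding appears in every setting.

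**The case against.** The strongest reply is that the investigators mean kappa on ADC above versus below a threshold. The hypothesis in section 1B speaks of a defined ADC threshold, the background quotes 2.0 × 10⁻³ mm²/s, and an ROC curve is planned. Both readers' values could be classified once a cut-off is known. That kappa would be interpretable: it runs from 0.99 down to 0.79 in the table and falls sensibly as reader error grows. Agreement on classification is also relevant to a study whose output is a threshold.

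This reading is reasonable, but the text does not state it. The 2.0 value is reported as an earlier study's result and is never tied to the kappa. The study's own threshold is still to be found; section 2d describes "an attempt to report a threshold ADC that reliably discriminates sterile and infected post-operative fluid collections". If classification agreement is meant, the cut-off or the rule for choosing it has to be written down.

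Two further points stand. Reader error moves kappa as well as rounding does, so rounding sets its level largely, not wholly. And unbiased readers with SD 0.10 may be optimistic: the Figure 1 observer means suggest systematic differences, which lower agreement without removing the dependence on rounding.

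It is also fair to say that this is one secondary descriptive statistic in a 20-patient pilot with no agreement target.

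**Conclusion.** The concern holds. As written, the plan applies a statistic for categories to a continuous measurement, and the resulting ADC kappa would not be interpretable as reliability. On the illustrative assumptions, readers with an ICC of 0.994 could be reported with a kappa anywhere from 0.02 to 0.98, depending on an unstated choice of rounding or cut-off. The exact values rest on the assumed reader error and on Figure 1; the dependence on rounding does not.

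The consequence is limited to the ADC reliability description that the pilot is meant to pass on to the larger study. Simple kappa for the five-point confidence score is valid. The statistic could be recomputed later if each reader's ADC values are kept, but section 9 does not say whether they will be. The change should be made before the readings are analysed, so that the categories are not chosen after the data are seen.

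**What to change.** In section 6c and in the Study Summary, restrict simple kappa to the confidence score (a weighted kappa there is optional). For ADC, specify:

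- a two-way, absolute-agreement, single-measure ICC with 95% CI; and
- Bland-Altman bias and limits of agreement in mm²/s,

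each reported separately for mean and 10th-percentile ADC.

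Rely mainly on the limits of agreement. The gap between infected and sterile groups raises the pooled ICC: at reader SD 0.10 it is 0.994 overall but 0.94 among abscesses alone.

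If agreement on the ADC classification is also wanted, state the cut-off, or the rule that will fix it, in advance and report simple kappa for above versus below it. State also that each reader's ADC values will be stored.

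The cost is one sentence in 6c and the matching sentence in the Study Summary. No new data, staff or patient burden is involved.
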